11.4 EEG

Because EEGs are optional and are intended to provide exploratory information only, no formal statistical analysis is planned. The analysis will depend on the amount and quality of data obtained.

12.0 DISCIPLINE REVIEW

See sections 9.2 and 9.4.

13.0 PHARMACOKINETICS

Not applicable.

14.0 LABORATORY CORRELATES

Not applicable.

15.0 MULTICENTER PROCEDURES

15.1 General Procedures

The BTTC Operations Manual and Data Submission Forms, on file at all BTTC institutions, document the data management and quality assurance programs for this collaboration. BTTC institutions will follow the guidelines as addressed below and throughout this protocol.

15.2 Principal Investigators

The principal investigator(s) will be responsible for the conduct of the study and monitoring its progress. The responsibility for all reports and forms required by BTTC will be that of the principal investigator(s).

15.3 Procedures for Patient Entry

15.3.1 Centralized Patient Registrations

Patients who are candidates for the study will first be evaluated for eligibility by the local investigator. All patients must be registered both locally and centrally with BTTC.

Before an institution may begin participating in a BTTC protocol, they must complete the following steps:

- Submit all required regulatory documents to the MDACC Office of Multicenter Clinical Research (OMCR) as outlined in the BTTC Operations Manual
- Participate in a site initiation visit, webcast, or conference call
- Receive training regarding study specific CRF's and/or databases

After these requirements have been fulfilled, the participating institution will receive by fax, e-mail, or hard copy memo a Site Activation Notification. Once the Site Activation Notification has been received, the participating institution may begin to register patients to the protocol

15.3.2 Patient Registration/Randomization

BTTC patients will be registered with the MD Anderson OMCR by fax & phone at UT MD Anderson. All eligibility requirements will be checked prior to registration. The status of all regulatory documents will be checked prior to registration. No patient will be entered on protocol if they do not satisfy all regulatory document and eligibility requirements. Generic MD Anderson OMCR registration procedures are also described in the BTTC Operations Manual.

Informed Consent/Authorization

Prior to protocol enrollment and initiation of treatment, subjects must sign and date an Institutional Review Board (IRB) approved consent form.

Patient Registration/Randomization Procedures

Participating institutions must register patients via EDMS, phone, and/or fax with the MD ANDERSON Office of Multicenter Clinical Research at:

EDMS: <https://iview.mdanderson.org/>

[contact]

[contact]

Email: [contact]

Registration hours are 8:00 a.m. to 5:00 p.m. Central Standard Time, Monday through Friday, except holidays.

Registrations must be completed after the patient has signed the informed consent and has been determined to be eligible by the local investigator.

At the time of registration the following information will be requested by the MDACC Office of Multicenter Clinical Research (OMCR):

- A faxed copy of a completed and signed, protocol specific, Eligibility Checklist form
- One copy of a Pathology report from the patient's most recent surgery or biopsy
- One copy of the signed and dated Informed Consent/Authorization.

The eligibility checklist form should be prepared and signed prior to faxing to the MD Anderson OMCR. The fax should be followed by a phone call to the MD Anderson OMCR to verify receipt. If the patient fails eligibility screening do not proceed to the registration process.

Patient Number for Participating Institutions

Once eligibility has been established during Registration, the patient from the participating institution is assigned a six character MD Anderson OMCR patient ID number and a protocol specific Accession Number. The patient ID number is unique to the patient and, except for SAE reports, must be used

for registrations onto subsequent protocols and written on all data and correspondence for the patient. The SAE reports must use the protocol specific Accession Number.

Verification of Registration/Randomization

For participating institutions, a Registration Verification Letter for patients registered to BTTC protocols will be faxed or emailed to the registering institution within one working day after the registration is received. The OMCR must be notified in advance of patient cases that may require an expedited registration.

Drug/Placebo Supply and Ordering

This protocol will use the DMI Drug Ordering /Randomization database housed at MD Anderson Cancer Center. Initial drug/placebo supply will be ordered by the Office of Multicenter Clinical Research (OMCR) after the pharmacist has submitted a Pharmacy Initiation Worksheet and the site have been activated for patient enrollment. Drug is ordered from Uintavision (UVI), a drug distributor. Once drug has been received the pharmacist must then send an email to the OMCR acknowledging receipt. When the supply is low for that institution, an automatic email is generated by the DMI Drug Ordering /Randomization database. The email is sent to the pharmacist as well as the OMCR. The OMCR will request re-supply from UVI. Again, the pharmacist must send the OMCR an email when drug is received.

When a site has been activated for patient enrollment, the pharmacist(s) receives a unique User Name and Password from the OMCR IT group that allows access to the DMI Drug Ordering/Randomization database. The pharmacist(s) must not share this information. After a patient has been enrolled, the OMCR also randomizes the patient to drug or placebo. This will also assign bottle numbers for that patient. The pharmacist receives an automatic email from the DMI Drug Ordering /Randomization database. The email contains a link to the database which allows the pharmacist to view the bottle numbers. When a patient is returning to clinic and needs a re-supply, the pharmacist notifies the OMCR via email or fax. The OMCR will then access the database and “request” bottle numbers. Again, the pharmacist is sent a link to the database which will allow them to view the bottle numbers assigned.

Contact information for OMCR:
MDACC Office of Multicenter Clinical Research
Attn: BTTC Project
[contact].
Email: [contact].

Initiation of Therapy

Treatment may not be initiated until the participating institution receives a faxed or emailed copy of the patient’s Registration Verification Letter from the MDACC OMCR.

All Patients that are eligible to receive therapy must initiate treatment within 14 days after the registration.

The MD Anderson OMCR must be notified in writing of any exceptions to this policy.

Eligibility Exceptions

Eligibility Exceptions will not be granted.

15.4 Data Management

All data will be entered remotely into the computerized data management system located at the MD Anderson OMCR at UT MD Anderson. Designated research staff from the registering institution will enter the data via remote electronic data entry. The protocol specific electronic forms are to be used by the participating sites. All investigators will utilize these forms for Baseline, Treatment, Tumor Evaluation, Off Treatment, Survival, and Off-study data.

Confidentiality

All documents, investigative reports, or information relating to the patient are strictly confidential. Any patient specific reports (i.e. Pathology Reports, MRI Reports, Operative Reports, etc.) submitted to the MD Anderson OMCR must have the patient’s full name & social security number “blacked out” and the assigned MD Anderson patient ID number and protocol number written in. Patient initials may be included or retained for cross verification of identification.

15.5 Data Monitoring

All submitted data will be monitored by the MD Anderson Protocol Manager specifically assigned to this protocol. Requests for correction of data deficiencies will be sent via mail to the Institutional Coordinator. Any major deficiencies will be corrected by telephone communication. All data will be monitored for completeness. Key parameters such as drug dosages including attenuations and escalations, toxicity documentation and tumor measurements will be analyzed. All data deficiencies will be corrected within two weeks.

The schedule for data & source document submission is outlined as follows.

Data Set / Source Documents	Schedule for Submission
Regulatory Documents (as described in the BTTC Operations Manual)	Prior to Patient Registration
Eligibility Checklist	Prior to Patient Registration
Copy of signed & dated Informed Consent w/ HIPAA Authorization	Prior to Patient Registration
Baseline Data (To include prior disease/treatment history, and baseline clinical evaluation information)	Within 14 days after the registration date
Baseline Source Documents	Within 14 days after the registration date
Baseline MDASI – BT Questionnaire	Within 14 days after the registration date

Treatment Data (To include treatment (reported in weekly increments), con meds, AE, and clinical evaluation information)	Within 14 days after each quarterly visit
Follow Up Data (the patient interim telephone contact)	Within 14 days after each follow up telephone call or clinic visit (includes the source document for patient interim telephone contact checklist form)
Treatment Source Documents (pill diaries, pill counts, physician orders/prescriptions)	Within 28 days after each quarterly visit
Off Treatment Data	Within 10 days after the last date of protocol treatment
Off Treatment Source Documents (if applicable)	Within 10 days after the last date of protocol treatment
Non-Treatment Data (May include Quality of Life questionnaires, EEG report, etc.)	Within 10 days after each scheduled assessment, event, or activity
Off Study Data	Within 10 days after the date the patient is removed from the study
Off Study Source Documents	Within 10 days after the date the patient is removed from the study
Pharmacy Drug Accountability Record Form Source Document	Within 10 days after the date the patient is removed from the study
Serious Adverse Events	Within 10 days after notification of SAE

15.6 Safety Assessments and Toxicity Monitoring

All patients receiving study agents will be evaluated for safety. The safety parameters include all laboratory tests and hematological abnormalities, CNS observations, physical examination findings, and spontaneous reports of adverse events reported to the investigator by patients. All toxicities encountered during the study will be evaluated according to the NCI Common Terminology Criteria for Adverse Events (CTCAE) version 4.0 and recorded quarterly or more often. Life-threatening toxicities that are unexpected and assessed to be possibly related to the study agent/s should be reported immediately to the study Coordinator, Institutional Review Board (IRB), and those that are unexpected and assessed to be possibly related to the study agents should also be reported to the FDA.

Information about all adverse events, whether volunteered by the subject, discovered by investigator questioning, or detected through physical examination, laboratory test or other means, will be collected and recorded on the Adverse Event Case Report Form and followed as appropriate. An adverse event is any undesirable sign, symptom or medical condition occurring after starting study drug (or therapy) even if the event is not considered to be related to study drug.

Medical conditions/diseases present before starting study treatment are only considered adverse events if they worsen after starting study treatment (any procedures specified in the protocol). Adverse events occurring before starting study treatment but after signing the informed consent form are recorded on the Baseline Evaluations Adverse Events Case Report Form. Abnormal laboratory values or test results constitute adverse events only if they induce clinical signs or symptoms or require therapy, and are also recorded on the Adverse Events Case Report Form.

Adverse events will be reported at least quarterly. In addition all serious adverse events will be reported to the study chair, and the MD Anderson OMCR as directed in section 15.7.

The MD Anderson Cancer Center DSMB will provide oversight for this protocol.

A serious adverse event is any adverse drug experience at any dose that results in any of the following outcomes: Death, a life-threatening adverse drug experience, inpatient hospitalization or prolongation of existing hospitalization, a persistent or significant disability/incapacity, or a congenital anomaly/birth defect. Important medical events that may not result in death, be life-threatening, or require hospitalization may be considered serious when, based upon appropriate medical judgment, they may jeopardize the patient or may require medical or surgical intervention to prevent one of the outcomes listed in this definition. Examples of such medical events include allergic bronchospasm requiring intensive treatment in an emergency room or at home, blood dyscrasias or convulsions in a patient who has never had seizure activity in the past that do not result in inpatient hospitalization, or the development of drug dependency or abuse.

Events *not* considered to be serious adverse events are hospitalizations for the purposes of this protocol and include:

- Routine treatment or monitoring of the studied indication not associated with any deterioration in condition.
- treatment, which was elective or pre-planned, for a pre-existing condition that did not worsen
- treatment on an emergency, outpatient basis for an event *not* fulfilling any of the definitions of serious given above and *not* resulting in hospital admission.

Pregnancy, although not itself a serious adverse event, should also be reported on a serious adverse event form and be followed up to determine outcome, including spontaneous or voluntary termination, details of birth, and the presence or absence of any birth defects or congenital abnormalities.

The study will utilize the Cancer Therapy Evaluation Program (CTEP) Common Terminology Criteria for Adverse Events (CTCAE) Version 4.0 for Toxicity and Adverse Event reporting. A copy of the CTCAE version 4.0 can be downloaded from the BTTC home page (<http://BTTC.cancer.gov/reporting/ctc.html>). All appropriate treatment areas should have access to either a hard copy of the CTCAE version 4.0 or the www version.

[figure not shown]
Serious Adverse Events will be reported via the BTTC SAE reporting process. **See section 15.7 for BTTC SAE reporting guidelines.**

Notification of Investigators of Expedited Adverse Events Reported to the FDA

The U.S. Food and Drug Administration (FDA) regulations require sponsors of clinical studies conducted under a U.S. IND to notify the FDA and all participating investigators of any serious and unexpected adverse experiences that are possibly related to the investigational agent. In compliance with these FDA regulations, BTTC will notify the BTTC affiliate investigators, via the MDACC Office of Multicenter Clinical Research, by the following methods:

[figure not shown]
IND Safety Reports –Investigators will be sent a copy of expedited adverse events, which BTTC has sent to the FDA. BTTC will notify consortium investigators via the MDACC Office of Multicenter Clinical Research. Within 7 business days of receipt of the notification the MDACC OMCR will forward the reports to the participating members with protocol specific instructions for IRB submissions, patient notifications, etc. For routine IND Safety Reports BTTC does not generally require an immediate revision to the master protocol and/or model informed consent documents maintained at the MDACC Office of Multicenter Clinical Research. The investigators are to file a copy with their protocol file and send a copy to their IRB according to their local IRB’s policies and procedures.

IND AE Action Letters - These letters are issued by BTTC for those serious adverse events, which warrant an immediate change in the informed consent form and/or protocol. Investigators will be sent a copy of expedited adverse events, which BTTC has sent to the FDA. BTTC will notify consortium investigators via the MDACC Office of Multicenter Clinical Research with the requirement that the model informed consent and or master protocol be amended to include the new event. Immediately upon receipt of the notification the MDACC OMCR will forward the letters to the participating members with protocol specific instructions for IRB submissions, patient notifications, etc. BTTC provides a time frame for which to submit the amendment to the BTTC Protocol and Information Office. The letter from BTTC will specify if accrual to the protocol is to be suspended until the revision is made and whether patients already on study require re-consenting.

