10.0 CRITERIA FOR REMOVAL FROM TREATMENT

10.1 Criteria for Removal from Protocol Treatment:

- a. Completion of one year of therapy.
- b. Unacceptable toxicity (**see Section 6.1.3**).
- c. Seizure (as defined in Section 9.1).
- d. The patient may voluntarily withdraw from treatment at any time for any reason.
- e. Medical or psychiatric illness which in the investigator's judgment renders the patient incapable of further therapy.
- f. Pregnancy.

All reasons for discontinuation of treatment must be documented in the flow sheets.

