11.0 STATISTICAL CONSIDERATIONS

11.1 Overview

The primary analysis for this study is a randomized, two-arm, parallel group, multicenter trial enrolling post-operative patients with newly-diagnosed high-grade glioma (HGG). Patients will be randomly assigned to either lacosamide (L) or placebo (P). Patients will be randomized to either treatment using a 1:1 randomization scheme. Based on a retrospective review of available data we assume a 20% seizure risk in the P group and 8% in the L group (after 1 year of observation). Based on these assumptions and assuming that time to first seizure follows an exponential distribution we estimate the hazard ratio between the L and P arms to be 0.374. Additional assumptions of the trial are that patients will be administratively censored after 1 year of follow-up and that 15% of patients will be lost to follow-up. The reason for the first assumption is that risk of seizure is greatest during the first year and as such clinical interest focuses on this time period. Because standard software packages do not incorporate administrative censoring we developed a SAS IML program to estimate the power associated with this clinical trial design.

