Based on this simulation program, the maximum fixed sample size to be accrued is 298 patients. The power for this analysis is 83.6% (power based on 1000 simulations). Because we plan 1 interim analysis using an O'Brien-Fleming stopping rule, we will need to adjust the sample size upward using the group sequential-to-fixed sample size ratio of 1.008 [35]. While this ratio is exact for trials with 80% power, it is a conservative lower bound for trials with greater than 80% power [35]. This ratio results in a trial with 302 patients (i.e., the largest even integer greater than 298×1.008). This results in a trial with 151 patients randomized to L and 151 patients randomized to P. The primary measure of efficacy is time to first seizure (TFS). The primary test of the difference in TFS between the treatment arms will be based on the likelihood ratio statistic for the treatment effect in a stratified proportional hazards regression model with anticonvulsant use as the stratification factor. The MDACC DSMB will periodically meet (either once every 6 months or annually) to evaluate safety and efficacy. The interim analysis will take place after 21 events have been observed. We will assess efficacy using an O'Brien-Fleming stopping rule with a nominal critical value of 2.7959 at the interim analysis. A futility analysis based on a conditional power assessment may be performed if the hazard ratio between the two treatment arms is approximately 1. If a conditional power assessment is performed and the conditional power is less than 0.10 the trial will be stopped for futility. The decision to perform this futility analysis will include an assessment of the number of events observed (i.e., at least 50% of the expected 42 events have occurred and all patients have not yet enrolled in the trial). If the study continues to full accrual, the final analysis will take place when all of the patients have either been followed for 1 year or have experienced a seizure event. We will test the null hypothesis $HR=1.00$ against $HR \neq 1.00$ at the 0.05 level. The conditional power for the time-to-event outcome will be computed based on the method described in Design and Analysis of Clinical Trials with Time-to-Event Endpoints (Peace 2009, page 60) and Lan Simon and Halperin (1982).

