Descriptive and inferential statistics will be used to summarize the treatment effects. The mean, standard deviation, median, 25% percentile, 75% percentile, minimum, and maximum will be reported for continuous variables by treatment group. For discrete (qualitative) outcomes, descriptive analyses will be based on the distribution of these discrete outcomes and will be reported as percentages and patient counts by treatment. Time to event endpoints will be descriptively summarized by Kaplan-Meier curves. Point and interval estimates of treatment effects will be based on maximum likelihood methods. For binomially distributed variables, we will report proportions, their 95% confidence intervals, differences in proportions and 95%

confidence intervals for the difference in proportions. Estimates of treatment effects for time to event endpoints will be based on the ratio of hazard functions (L: P) using Wald type scores from a Cox proportional hazards regression model. Unless stated otherwise, all statistical tests will be assessed using a two-sided $\alpha = 0.05$ significance level and confidence intervals will be constructed using two-sided 95% and will be based on the normal approximation. Although multiple secondary endpoints will be evaluated we will make no adjustment for multiplicities associated with these multiple tests.

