11.2.5 Adverse Events

Clinical and laboratory adverse events will be coded using the NCI's Common Terminology Criteria for Adverse Events (CTCAEv4.0). The CTCAEv4.0 will be attached to the clinical database.

Summaries of unique adverse events will include

- all treatment emergent adverse events,
- all treatment emergent adverse events by the worst grade,
- all related treatment emergent adverse events,
- all related treatment emergent adverse events by the worst grade,
- all adverse events leading to study drug discontinuation

Treatment emergent adverse events are

- Events with onset dates on or after the start of treatment and up to 30 days after the permanent discontinuation of the study medication
- Continuing adverse events diagnosed before the start of treatment and getting worse in grade or relationship to treatment after the start of treatment.

Related adverse events include all those classified by the investigator as definitely, probably, or possibly related to the study drugs. Events for which the investigator did not record relationship to study drug will be considered related to study drug.

Multiple events will be counted once only per patient in each summary. In the presentation, Adverse Event Categories will be sorted in alphabetical order. Within Categories adverse events will be sorted in descending order of total events. For summaries by severity, the most severe event will be selected.

Deaths and serious adverse events

Serious adverse events and deaths will be listed. Data from the adverse event page that specify the event is serious will be used to generate the listing.

Summaries of serious unique adverse events will include:

- all serious treatment emergent adverse events,
- all related serious treatment emergent adverse events by the worst grade,

11.3 Patient Reported Outcomes.

The sample size for this trial was based on the primary endpoint of the study.

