15.7 Guidelines for Reporting Serious Adverse Events to BTTC

All patients receiving agents will be evaluated for safety. Local IRB SAE reporting procedures are to be followed by all Institutions. At the same time all SAEs must also be reported to the Lead Principal Investigator and the BTTC Coordinating Center.

BTTC SAE reporting requirements and time frames for reporting to the BTTC Coordinating Center are described below:

Adverse Event Reporting for Investigator-Initiated Clinical Trials			
UNEXPECTED EVENT		EXPECTED EVENT	
Grade 2 & 3	Grades 4 and 5	Grades 1-3	Grades 4 and 5
Attribution of Possible, Probable or Definite	Regardless of Attribution		Regardless of Attribution

Expedited report to MDACC OMCR within 5 working days.
	
Report by phone to MDACC OMCR Within 24 hrs. Expedited report to follow within 5 Working days.
	
Adverse Event Expedited Reporting is NOT required.
	
Expedited report, including Grade 5 Aplasia in leukemia patients, within 5 Working days.

Grade 1 – Adverse Event Expedited Reporting not required.
	
This includes deaths within 30 days of the last dose of treatment with an investigational agent regardless of attribution. Any late death attributed to the agent (possible, probable, or definite) should be reported within 5 working days.
		
This includes deaths within 30 days of the last dose of treatment with an investigational agent regardless of attribution. Any late death attributed to the agent (possible, probable, or definite) should be reported within 5 working days. Grade 4 Myelosuppression or other Grade 4 events that do not require expedited reporting will be specified in the protocol.

For Hospitalization Only – Any medical event equivalent to CTC Grade 3, 4, 5 which precipitated hospitalization (or prolongation of existing hospitalization) must be reported regardless of requirements for phase of study, expected or unexpected and attribution.
			

Expedited reporting may not be appropriate for specific expected AEs for certain later Phase II and Phase III protocols. In those situations the AE that will not have expedited reporting must be specified in the text of the approved protocol.
			

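### The safety summaries do not say how to treat endpoint seizures, so per-patient totals can net seizure prevention against lacosamide intolerance

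*Combined protocol and SAP*

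**What the plan says.** **Endpoint.** Section 11.1 states: "The primary measure of efficacy is time to first seizure (TFS". Section 9.1 defines seizure to include simple partial, complex partial and secondarily generalised events, and section 9.2 has a blinded Clinical Event Committee classify each event.

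**Adverse event.** Section 15.6 counts any unwanted sign, symptom or condition that arises after study drug starts, whether or not it is related. Endpoint seizures are not exempted.

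**Serious adverse event.** Section 15.6 allows important medical events to be classed as serious on medical judgment. Its examples include "blood dyscrasias or convulsions in a patient who has never had seizure activity in the past that do not result in inpatient hospitalization".

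**End of treatment.** The list of removal criteria in section 10.1 has, as item c, "Seizure (as defined in Section 9.1". Unacceptable toxicity is item b.

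**Safety summaries.** Section 11.2.5 plans summaries of treatment-emergent events, of serious treatment-emergent events, and of "all adverse events leading to study drug discontinuation". A patient counts once in each summary, and the presentation is by category and by event within category. The section gives no rule for endpoint seizures.

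**Related tables.** Section 11.2.4 separately summarises the reasons for stopping study drug. Section 11.2.5 also has summaries limited to related events, in which an event with no recorded causality counts as related.

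**The concern.** The same event can enter the efficacy analysis as the outcome and the safety tables as harm. If lacosamide works, these events fall mainly in the placebo arm. A per-patient count that mixes seizures with toxicity then moves in lacosamide's favour because the drug prevents the endpoint, not because it is better tolerated. The more effective the drug, the larger the distortion.

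The summary of adverse events leading to discontinuation is the most exposed, because every protocol seizure is also a reason to stop treatment. The documents do not say whether a stop under 10.1(c) is also recorded as an adverse event leading to discontinuation. Sites could code it either way, so the share of seizures in that count is uncontrolled. The data safety monitoring board reviews both safety and efficacy (11.1), so mixed totals could also reach it during the trial.

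**Working it through.** **Inputs**
- Seizure risk (11.1): "we assume a 20% seizure risk in the P group and 8% in the L group (after 1 year of observation". Call these s_L = 0.08 and s_P = 0.20.
- Discontinuation for adverse events in the earlier controlled trials (2.5): 17% at 400 mg/day, 8% at 200 mg/day, 5% on placebo. The target here is 200 mg twice daily, which is 400 mg/day (6.2.1.4). Call these t_L = 0.17 and t_P = 0.05.
- Patients per arm (11.1): 151.
- Not in the documents: f, the share of seizures recorded as adverse events leading to discontinuation. It is varied from 0 to 1.

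**The plan's own figures**
- ln(0.92)/ln(0.80) = 0.3737, which agrees with 11.1: "we estimate the hazard ratio between the L and P arms to be 0.374".
- Simulating the likelihood-ratio test with 298 patients, one-year censoring and 15% loss gives 82.9% power, against 83.6% stated. The design inputs are sound, and nothing below changes them.

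**Discontinuation count**

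Treating toxicity and seizure as independent, the proportion of patients counted in an arm is 1 - (1 - t)(1 - f x s). Power is for a two-sided 0.05 comparison of two proportions with 151 per arm. It measures visibility only, since the plan specifies no such test.

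| f | Lacosamide | Placebo | Difference (points) | Power |
|---|---|---|---|---|
| 0 | 17.0% | 5.0% | +12.0 | 92% |
| 0.25 | 1 - 0.83 x 0.98 = 18.7% | 1 - 0.95 x 0.95 = 9.8% | +8.9 | 60% |
| 0.50 | 1 - 0.83 x 0.96 = 20.3% | 1 - 0.95 x 0.90 = 14.5% | +5.8 | 27% |
| 0.75 | 1 - 0.83 x 0.94 = 22.0% | 1 - 0.95 x 0.85 = 19.3% | +2.7 | 9% |
| 1 | 1 - 0.83 x 0.92 = 23.6% | 1 - 0.95 x 0.80 = 24.0% | -0.4 | none |

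In patients, f = 0 is about 26 against 8 of 151 (difference 95% CI 5.1 to 18.9 points). At f = 1 it is about 36 against 36 (95% CI -10.0 to 9.2).

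**Sensitivity**
- With the 8% rate cited for 200 mg/day, the difference goes from +3.0 points at f = 0 to -8.6 at f = 1.
- With no seizure effect (20% in both arms), f = 1 gives 33.6% against 24.0%, or +9.6 points. The cancellation therefore comes from efficacy.

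**Serious events (upper bound)**

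The documents give no background rate of serious events. Assume it is equal in both arms, at a value b between 5% and 30%, and that every seizure is classed as serious. The difference is then -(1 - b) x 0.12, so placebo is higher by 11.4 points (b = 5%) to 8.4 points (b = 30%). The real shift is smaller to the extent that seizures are not classed as serious.

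**The case against.** The strongest reply is that the plan already shows intolerance elsewhere. Section 10.1 separates seizure from toxicity and 11.2.4 summarises the reasons for stopping, so toxicity stops can be read apart from seizure stops. Section 11.2.5 reports by event and in summaries limited to related events, and dizziness, ataxia or diplopia would appear in their own rows. No all-events arm total and no between-arm test of adverse events is specified. Full cancellation also needs every seizure to be coded as an adverse event leading to discontinuation.

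Much of this stands, and it limits the point to any-event and category-level counts. It does not remove it. Nothing says that a stop under 10.1(c) stays out of the 11.2.5 summary. A per-patient count without seizures cannot be rebuilt by subtracting rows, because patients overlap. A seizure with no recorded causality would enter the related summaries. Partial coding already matters: at f = 0.5 about half of the excess is gone.

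A reader might infer more than the documents support:
- *Every endpoint seizure is a serious event.* Section 15.6 leaves this to judgment. Its example covers convulsions in patients with no past seizure, whereas 9.1 includes non-convulsive seizures and 4.18 admits patients whose last seizure was more than 10 years ago.
- *Every endpoint seizure is counted twice.* The treatment-emergent window closes 30 days after permanent discontinuation, so a later seizure can count for efficacy only.
- *Section 9.3 makes discontinuation the main tolerability measure.* It concerns patient-reported symptoms and their interference with daily life.
- *Section 15.7 already requires seizures to be named.* Its sentence "In those situations the AE that will not have expedited reporting must be specified in the text of the approved protocol" applies only where expedited reporting is waived, and the protocol claims no such waiver.

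**Conclusion.** The point holds as a gap in the safety reporting rules. Nothing in 11.2.5 or 15.6 keeps endpoint seizures out of the treatment-emergent, serious or discontinuation summaries, so any-event and category-level per-patient counts can mix benefit with harm. On the documents' rates, a 12-point excess of discontinuation on lacosamide would appear as anything from +8.9 to -0.4 points as the recorded share of seizures runs from 25% to 100%.

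This rests on three assumptions: independence of toxicity and seizure, the planned seizure effect, and tolerability rates carried over from add-on epilepsy trials with 12-week maintenance. The documents give no one-year rate in glioma. It would go too far to say that intolerance is hidden throughout the safety tables, since several planned displays would still show part of it. The primary analysis, sample size and power are not affected. This is an inexpensive improvement, not a flaw in the design.

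**What to change.** In 11.2.5, present the treatment-emergent, serious and discontinuation summaries twice, once including and once excluding seizures classified as such by the Clinical Event Committee (9.2). Tabulate those seizures separately by arm. In 15.6, state that protocol seizures are flagged as endpoint events on the adverse event form.

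Both presentations should stand side by side. Whether the seizure-excluded version should be the main one is debatable, because a seizure can itself be a harm of treatment: 6.3 warns of seizure when an antiepileptic drug is stopped suddenly.

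The cost is a few sentences of plan text, one flag built on data already collected, and one extra set of safety tables.
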